Official title: Adherence to Care for Children With Congenital Zika Virus Infection in Puerto Rico

NCT number: NCT05041439

Document date: 08/18/2023

Adherence to Care for Children With Congenital Zika Virus Infection in Puerto Rico

NCT05041439

August 18, 2023

PI: [name], MPhil, MPH

R21HD096369

Brief Study Protocol and Methods

Official title: Adherence to Care for Children With Congenital Zika Virus Infection in Puerto Rico

NCT number: NCT05041439

Document date: 08/18/2023

Puerto Rico Department of Health (DOH) guidelines for follow-up of children with possible congenital Zika virus infection recommend developmental monitoring every 6 months from 12 to 60 months of age. We conducted a pilot randomized trial of *Aquí Para Ti*, a 5-session theory-based psychosocial intervention delivered by a community health worker that uses a problem-solving approach and tailored health communication tools to improve adherence to pediatric care.

Intervention design

We recruited caregiver-child dyads to observe outcomes in both. We randomly assigned 50 caregiver-child dyad participants through computer-generated allocation sequence to either the intervention (n=25) or an enhanced control condition (n=25) (ECC). This sample size is consistent with recommendations for randomized pilot studies for preliminary estimation of effect sizes and lower bounds. Randomization occurred at the level of the individual participant, stratified by clinic and the presence or absence of congenital abnormality in the child at the time of enrollment.

Community health worker (CHW) group: The intervention, *Aquí Para Ti*, is delivered by community health workers (CHWs). In this pilot randomized trial, the CHW was a Spanish-speaking clinical research coordinator with experience in public health and a bachelor's degree. Study staff devoted significant time to training the CHW in the intervention protocol. Members of the study staff who developed the intervention were an infectious diseases physician, psychologist, and pediatrician/neonatologists. They trained the CHW in the intervention manual. Due to public health requirements of the COVID-19 public health emergency, CHW training occurred by video conference and involved training in HIPAA-compliance, basic neurodevelopment, congenital Zika virus infection, and the intervention manual. Training occurred through didactic sessions, role-playing, and audio recording of practice sessions with opportunities for feedback. CHWs were supervised in weekly one-hour sessions by videoconference, which allowed for problem-solving issues raised in the sessions.

Participants randomized to the intervention received 5 one-hour sessions with the CHW over six months. Sessions occurred by video conference due to the COVID-19 pandemic public health restrictions. Each session focused on barriers to pediatric Zika services that were raised in our preceding qualitative research. Session 1 is an orientation to the program and focuses on setting goals and balancing priorities. Session 2 focuses on understanding the importance of pediatric care, child development, and the role of the Ages and Stages Questionnaire in monitoring child development. Session 3 focuses on communicating with the pediatrician. Session 4 focuses on training the caregiver in skills for telehealth. Session 5 focuses on reviewing themes from the prior sessions to prepare for future barriers to adherence to pediatrics services.

At each session, the CHW elicits the participant's knowledge (e.g. importance of adherence to pediatric services, caregiver burden, perceived need for pediatric care). The CHW evokes and selectively reinforces the participant's self-motivational statements, focusing on empathy, eliciting change talk, addressing barriers through problem-solving, and promoting self-efficacy. A key feature is the development of activation and self-efficacy to engage in adherence so that participants can sustain adherence behavior. Each visit closes with defining action steps and practice assignments (e.g. finding transportation, meeting with the pediatrician). The sessions incorporate multimedia health communication content developed by the research team with a multimedia company based on formative research with caregivers of children with congenital Zika virus infection in Puerto Rico and their providers. The health communication tools focus on barriers to Zika services and communication with pediatric providers.

Enhanced care condition (ECC): In ECC, participants receive brief five locator outreach calls over 6 months. The CHW also offers printed educational material from the Puerto Rico Department of Health on child development. No navigation services are provided. We chose an ECC design with a general wellness component to reduce the likelihood that intervention effects detected in the intervention arm were not due to nonspecific characteristics such as interaction with study staff.

Official title: Adherence to Care for Children With Congenital Zika Virus Infection in Puerto Rico

NCT number: NCT05041439

Document date: 08/18/2023

Data elements: The primary outcome was attendance in ≥ 1 routine pediatric appointment in months 0–6 post-randomization. The secondary outcomes were attendance in routine pediatric care in both months 0–6 and 7–12 and detection of a new Zika-associated neurodevelopmental abnormalities at months 0–6 and 0–6 and 7–12. An appointment was defined as a routine outpatient pediatric appointment for neurodevelopmental monitoring. A neurodevelopmental abnormality was based on consensus guidelines from the University of Puerto Rico School of Medicine Medical Sciences Department of Pediatrics and Puerto Rico Department of Health criteria, which were based on Centers for Disease Control definitions of anomalies possibly associated with congenital Zika virus infection. Medical records were from the Puerto Rico Department of Health and the University of Puerto Rico Medical Sciences Campus High Risk Clinic in the Department of Pediatrics. Two independent reviewers blinded to participant allocation extracted outcomes from medical records.

Statistical analysis: Participant sociodemographic and clinical characteristics were summarized by intervention allocation with Chi-square tests and t-tests. The primary analysis used the intention-to-treat approach. The primary analysis compared those randomized to the intervention compared with those randomized to the enhanced control condition. We compared the detection rate of a new birth defect or neurodevelopmental abnormality possibly associated with congenital Zika virus infection for each participant from baseline to month 6 and baseline to month 12 using Fisher's exact tests.

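### Does the reversed wording of the control-arm rationale, or the shorter staff contact in that arm, call for a change to the plan?

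*Combined protocol and SAP*

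**What the plan says.** The section Enhanced care condition (ECC) describes the comparator in a few sentences. On contact: "In ECC, participants receive brief five locator outreach calls over 6 months". On content: "The CHW also offers printed educational material from the Puerto Rico Department of Health on child development". It adds that navigation is not offered. The rationale then begins "We chose an ECC design with a general wellness component" and gives the purpose: "to reduce the likelihood that intervention effects detected in the intervention arm were not due to nonspecific characteristics such as interaction with study staff".

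The section Community health worker (CHW) group describes the other arm: "Participants randomized to the intervention received 5 one-hour sessions with the CHW over six months". On format: "Sessions occurred by video conference due to the COVID-19 pandemic public health restrictions".

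The section Intervention design calls the comparator "an enhanced control condition (n=25) (ECC"), and the Statistical analysis section also uses control, whereas the ECC section heading uses care. Intervention design explains the 50 dyads this way: "This sample size is consistent with recommendations for randomized pilot studies for preliminary estimation of effect sizes and lower bounds".

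**The concern.** Four things stand out in the ECC text.

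- **Reversed purpose.** Lowering the chance that an effect is not due to staff interaction means raising the chance that it is. That is the opposite of why contact is added to a control arm, and no other sentence in the document says what the comparator controls for.
- **Partial matching.** Even read as intended, the ECC does not equalise staff time: brief calls are set against one-hour sessions. An effect could partly reflect attention rather than the programme's content.
- **Undescribed component.** A general wellness component is named once, while the only content listed is printed child-development material.
- **Two names** for one arm.

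What would be at stake is interpretation. The pilot is sized to give preliminary effect sizes, presumably for later use. Someone planning a later trial with a comparator closer in contact time would be estimating a different contrast, and the rationale sentence does not say so.

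**Working it through.** The protocol states no total contact time, so there is no figure to reproduce. The check is one of logic, then simple arithmetic, then a look at what the analysis uses.

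**1. The sentence.** Let *p* be the chance that a detected effect is due to nonspecific features. As printed, the ECC is meant to lower 1 − *p*, which raises *p*. But the ECC as described gives controls their own staff contacts. Whatever contact the arms share cancels from the comparison, which can only lower *p*. The printed reading therefore contradicts the design described just before it, and dropping the second negative restores agreement. Only one reading is workable.

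**2. Contact, side by side.**

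| Feature | Intervention | ECC | Matched? |
|---|---|---|---|
| Number of contacts | 5 | 5 | Yes |
| Period | 6 months | 6 months | Yes |
| Staff | CHW | CHW named as offering the printed material | Apparently |
| Length | 60 minutes each | Brief, minutes not given | No |
| Medium | Video conference | Calls, medium not named | Cannot be told |

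**3. Contact time.** Total = number of contacts × minutes per contact.

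- Intervention: 5 × 60 = 300 minutes.
- ECC call length needed to match: 300 / 5 = 60 minutes, which the word brief rules out.
- ECC at an assumed 5 minutes: 5 × 5 = 25 minutes, a gap of 275 and a ratio of 12.
- ECC at an assumed 15 minutes: 5 × 15 = 75 minutes, a gap of 225 and a ratio of 4.
- ECC at an assumed 30 minutes: 5 × 30 = 150 minutes, a gap of 150 and a ratio of 2.

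The direction of the gap comes from the protocol. Its size comes only from the assumed call lengths, and nothing in the document converts minutes into a difference in attendance.

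**4. What the analysis uses.** The primary comparison is by intention to treat, between the arms as randomised. The outcomes are attendance and new abnormalities, extracted from medical records by two reviewers blinded to allocation. Detection is compared by Fisher's exact test. None of these takes the rationale sentence, call length or comparator label as an input. Because the outcomes come from records, extra staff contact could matter only by changing real attendance or detection, not by changing what caregivers report.

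**5. The labels.** The wellness component is mentioned two sentences after the printed material, and no other content is listed, so that material is its natural referent. The two names share one abbreviation in a two-arm trial, so the arm cannot be mistaken.

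**The case for a change.** The best case for acting is that this is the sole statement of what the comparator is for, it is printed backwards, and correcting it would still leave call length and the wellness component unstated. Because the sample size rests on preliminary effect estimation, a reader may carry the estimate into a later design without noticing that it includes extra staff time. A few sentences would fix that, with nothing new to collect.

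Part of this stands. The wording is wrong, the component is loosely labelled, and staff time is not matched.

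The rest does not amount to a fault in the plan. The rationale speaks of reducing a likelihood, so it claims neither full control nor matched time. The facts that limit it are disclosed: one-hour sessions on one side; brief calls, printed material and no navigation on the other. Problem-solving, eliciting change talk and building self-efficacy are the specific intervention; a control for nonspecific effects is supposed to lack them, so their absence is not a shortfall. A mismatch between video and telephone is an inference, since the medium of the calls is not stated. To say the estimate transfers only to trials with similarly little control contact presumes that contact alone changes attendance, which the document cannot show. Every trial effect is relative to its comparator, and how closely to match attention in a 50-dyad pilot of a CHW-delivered package is a reasonable design choice.

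**Conclusion.** No change to the plan follows. The second negative is a clerical slip whose intended meaning is plain from the design around it. The two names and the loosely labelled wellness component are matters of copy-editing and brief description that a reader resolves without difficulty. Unequal contact time is a fair trade-off, already visible in the protocol: five contacts over six months in each arm, with 300 planned minutes in the intervention arm and an unstated smaller total in the ECC. The trial estimates the effect of the whole package, content plus contact, against the ECC, and that contrast is valid under intention to treat.

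The effect on any estimate, test or sample-size figure is nil. This rests on two readings: that brief means shorter than an hour, and that the rationale was meant in the usual sense of a control for attention. The 2- to 12-fold ratios depend on assumed call lengths of 5 to 30 minutes, and the conclusion does not use them.

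### Does the Fisher's exact test count a wider event (birth defects as well) than the secondary detection outcome that the plan declares?

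*Combined protocol and SAP*

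**What the plan says.** Three places in the combined protocol and SAP bear on this.

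- **Data elements, outcome.** The secondary detection outcome is "detection of a new Zika-associated neurodevelopmental abnormalities at months 0–6 and 0–6 and 7–12".
- **Data elements, criteria.** The next sentences give the source of the criteria: "A neurodevelopmental abnormality was based on consensus guidelines from the University of Puerto Rico School of Medicine Medical Sciences Department of Pediatrics", together with Department of Health criteria. Both rest on federal definitions of anomalies possibly linked to congenital Zika infection. Two reviewers blinded to allocation extracted outcomes from medical records.
- **Statistical analysis.** "We compared the detection rate of a new birth defect or neurodevelopmental abnormality possibly associated with congenital Zika virus infection for each participant", over two windows, baseline to month 6 and baseline to month 12, by Fisher's exact test.

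The Intervention design section uses a further term, for randomization only: "stratified by clinic and the presence or absence of congenital abnormality in the child at the time of enrollment". It also gives the basis for 25 dyads per arm, which is advice for "randomized pilot studies for preliminary estimation of effect sizes and lower bounds".

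**The concern.** The outcome sentence names neurodevelopmental abnormalities. The test sentence puts birth defect beside that term, joined by *or*, so on its face the tested event is a composite and the declared one is not. The criteria sentence attaches its sources to the neurodevelopmental term alone. Read literally, the plan does not say whether a child whose only new record is a birth defect counts as an event.

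This is the only test the plan names for an outcome; the chi-square and t-tests are for participant characteristics. If the declared and tested events differed, the reported detection rates would not estimate the declared outcome. In a trial sized for preliminary effect estimates, a single child could shift the estimate and its lower bound noticeably.

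**Working it through.** **1. A figure to reproduce.** The plan states no power, alpha or event rate for this outcome. The only checkable arithmetic is the allocation, 25 + 25 = 50, which agrees.

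**2. The labels side by side.**

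| Place | Event named | Criteria attached |
|---|---|---|
| Data elements, outcome | New Zika-associated neurodevelopmental abnormality | Given in the same paragraph |
| Data elements, criteria | Neurodevelopmental abnormality | University and Department of Health criteria, from definitions of Zika-associated anomalies |
| Statistical analysis | New birth defect or neurodevelopmental abnormality, possibly Zika-associated | None separately |
| Intervention design | Congenital abnormality at enrollment | Stratification factor, not an endpoint |

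The root of the criteria is a definition of *anomalies*, a broader word than *neurodevelopmental*. The test sentence repeats the same possible-association qualifier. One criteria set and one extraction are described. The simplest reading is one endpoint with a short label in one sentence and a longer label in the other. The document does not state this, so it remains an inference.

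**3. What makes an event new.** The stratification wording does not leave this open. The analysis sentence counts events "for each participant from baseline to month 6 and baseline to month 12", so the reference point is baseline. The second window in the outcome sentence is clumsy, but it most naturally means cumulative detection to month 12, which is how the analysis sentence puts it.

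**4. How much one child could matter.** Event counts are assumed, since the documents give none. With n = 25 per arm, one child is 1/25 = 0.04. Each row removes one intervention-arm child whose only event is a birth defect. The difference is d = t/25 − c/25, for t intervention and c control events. P-values are two-sided Fisher exact; lower bounds are from the Newcombe (Wilson-based) 95% interval.

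| Events (intervention vs control) | Difference, points | Lower bound, points | Fisher p |
|---|---|---|---|
| 6 vs 0 → 5 vs 0 | 24 → 20 | 5.7 → 2.6 | 0.022 → 0.050 |
| 6 vs 1 → 5 vs 1 | 20 → 16 | +0.1 → −3.1 | 0.098 → 0.190 |
| 9 vs 2 → 8 vs 2 | 28 → 24 | 4.8 → 1.5 | 0.037 → 0.074 |
| 4 vs 2 → 3 vs 2 | 8 → 4 | −11.5 → −14.7 | 0.67 → 1.00 |
| 5 vs 3 → 4 vs 3 | 8 → 4 | −13.1 → −16.4 | 0.70 → 1.00 |

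The first three rows sit close to a conventional line; the last two do not. Over all tables with more intervention than control events there are 25 × 26 / 2 = 325 pairs. Removing one intervention event takes p from below 0.05 to 0.05 or above in 20 of them (20/325 = 6.2%, with every table weighted equally). The plan sets no alpha, so even those crossings have no formal standing.

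**5. What the table shows.** The 4-point step is a property of any binary outcome with 25 per arm. It says nothing about whether this label led any child to be classified differently.

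**The case for a change.** The strongest case for a change is that one of the two sentences must be imprecise under either reading. If the criteria include birth defects, the outcome sentence under-describes the endpoint. If they do not, the test counts events outside the declared outcome. A reader cannot reproduce the test without knowing which holds, effect estimation is the pilot's stated purpose, and the remedy is cheap.

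The first part stands: the labels differ, and a clear report should say which events were counted. The step from there to a change in the plan does not stand. Extraction is described in the past tense, so rewording would record what was done and would not alter what is counted or compared. Testing only the neurodevelopmental part, with birth defects as a separate count, would presume that the criteria exclude birth defects, which the documents do not show. Adding a confidence interval beside the p-value may be sensible, but it is a separate matter that the label does not raise.

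**Conclusion.** The mismatch is a loose label in a brief protocol, not a demonstrated analysis error. The reading that one criteria set covers both terms rests on the shared qualifier and on the single extraction described; the cited criteria would be needed to confirm it.

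The possible effect is 4 percentage points per reclassified child. It is zero if the criteria already cover birth defects, or if no child had a birth defect as the only new record. The actual size cannot be derived, because no event counts are given. The point is confined to a secondary outcome of a 50-dyad pilot and does not reach the primary attendance outcome. Analysts holding the extraction records can settle the label when they report, so no change to the plan follows.

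### Randomisation is stratified by clinic and congenital abnormality, but no stated analysis uses the strata; if they are prognostic, the pooled Fisher test is needlessly conservative

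*Combined protocol and SAP*

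**What the plan says.** Under Intervention design, 50 caregiver-child dyads are allocated 25 to each arm, "stratified by clinic and the presence or absence of congenital abnormality in the child at the time of enrollment". The number of clinics, the stratum sizes and the blocking method are not given. The sample size is justified as suitable for "preliminary estimation of effect sizes and lower bounds"; no power, alpha or event rates are stated.

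The Statistical analysis section contains three things:

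- **Baseline:** "Participant sociodemographic and clinical characteristics were summarized by intervention allocation with Chi-square tests and t-tests".
- **Primary analysis:** intention to treat, described only as "The primary analysis compared those randomized to the intervention compared with those randomized to the enhanced control condition". No test, model, effect measure or interval is named for attendance.
- **Detection (secondary):** a comparison of arms "from baseline to month 6 and baseline to month 12 using Fisher's exact tests".

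No stratified test, adjusted model or stratum term appears for any outcome.

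**The concern.** Balancing the arms within strata removes between-stratum differences from the sampling variation of the arm contrast. A single 2×2 table of all 50 children puts that variation back into the reference distribution. If the strata predict the outcome, the pooled test rejects less often than its nominal level allows, and an interval built from the pooled table is too wide.

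This matters because the pilot's stated product is an effect size and its lower bound. An interval that is too wide sets that bound too low, and the detection test loses power. Prognostic strata are plausible but not documented: one factor is abnormality at enrolment while the tested outcome is a new abnormality, and clinic could affect attendance.

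**Working it through.** **Inputs from the document.** 25 per arm; two stratification factors; Fisher's exact test for detection. There is no power calculation to reproduce.

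**Assumptions.** Two-sided 5% level; two strata of 13 and 12 per arm with exact balance; the event rates below.

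**Variance.** Let stratum *s* have n_s children per arm.

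- Pooled: V_pool = [p̄_C(1−p̄_C) + p̄_I(1−p̄_I)]/25
- Balanced within strata: V_strat = Σ n_s[p_Cs(1−p_Cs) + p_Is(1−p_Is)]/25²

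Example: control 20%/70%, intervention 50%/95%.

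- p̄_C = (13×0.20 + 12×0.70)/25 = 0.440; p̄_I = (13×0.50 + 12×0.95)/25 = 0.716
- V_pool = (0.2464 + 0.2033)/25 = 0.01799, SE 0.134
- V_strat = [13(0.16+0.25) + 12(0.21+0.0475)]/625 = 8.42/625 = 0.01347, SE 0.116
- Ratio 0.134/0.116 = 1.16; half-widths 1.96×SE = 26.3 and 22.7 points

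With 50% to 80% in both strata, both variances are (0.25+0.16)/25 = 0.0164 and the ratio is 1.

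**Simulation**, 20,000 replicates per scenario (error about 0.35 points on power). The exact stratified test convolves the stratum hypergeometric distributions. SE ratio is mean pooled SE over the true SD. Half-widths are means, in percentage points.

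| Control → intervention | Power: Fisher / stratified | SE ratio | 95% half-width: pooled / Mantel-Haenszel | Type I error: Fisher / stratified |
|---|---|---|---|---|
| 50% → 80%, both strata | 51.1 / 51.4% | 0.98 | 24.5 / 24.5 | 3.3 / 3.3% |
| 40%/60% → 70%/85% | 43.6 / 44.6% | 1.00 | 25.0 / 24.6 | 2.8 / 2.8% |
| 30%/70% → 60%/90% | 35.6 / 39.7% | 1.06 | 25.5 / 23.6 | 2.1 / 2.6% |
| 20%/70% → 50%/95% | 42.0 / 50.7% | 1.14 | 25.9 / 22.2 | 1.3 / 2.2% |
| 20%/80% → 50%/95% | 25.9 / 37.4% | 1.19 | 26.0 / 21.6 | 0.7 / 1.9% |

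The power gains are 0.3, 1.0, 4.1, 8.7 and 11.5 points. The half-widths differ by 0, 0.4, 1.9, 3.7 and 4.4 points. Exact enumeration agrees: 51.0 vs 51.3%, 35.2 vs 39.1%, 42.0 vs 50.8% and 26.0 vs 37.8% for rows 1, 3, 4 and 5.

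**Unequal strata (20 and 5 per arm).** The two strong cases gain about 4 and 5 points (46.8 vs 50.5%; 40.4 vs 45.5%); the other three gain under 1.

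**Rare events (13 and 12 per arm).** 5%/15% → 25%/40% gives 36.9 vs 37.7%. 5% → 30% in both strata gives 54.7 vs 52.2%, a loss for the stratified test.

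**Is the cause the strata, or Fisher's discreteness?** At a control rate averaging about 30%, exact enumeration gives:

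| Control rates | Fisher null rejection | Power at odds ratio 4: Fisher / stratified |
|---|---|---|
| 30%/30% | 0.0229 | 0.600 / 0.600 |
| 20%/40% | 0.0194 | 0.546 / 0.549 |
| 10%/50% | 0.0108 | 0.345 / 0.409 |
| 5%/55% | 0.0060 | 0.171 / 0.314 |

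With the same overall rates but unstratified randomisation, Fisher's null rejection stays at 0.022 to 0.023. The further fall therefore comes from ignoring the strata. The shortfall from 5% that remains is discreteness, which an exact stratified test does not remove.

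**The case against.** The strongest reply is that nothing stated in the plan is invalid. Fisher's test controls type I error, it is named only for a secondary outcome, and every rate behind the loss is assumed. Under weak prognosis the gain is negligible, and with rare events it can be negative. The plan states no interval, so none is yet too wide. With equal arms within strata the Mantel-Haenszel and pooled risk differences coincide, so the point estimate does not change. Clinic-by-abnormality cells may also be sparse among 50 children. All of this stands, and it makes the point one of efficiency rather than validity.

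A second reply is that the extra conservatism depends on tight balance within strata, while the blocking method is not stated. If balance is left to chance, pooled Fisher's type I error in the 20%/80% case returns to 3.3% and the SE ratio to 0.98. But stratified randomisation is meant to prevent that. With permuted blocks of 4 or 6 within strata, Fisher's type I error stays at about 0.8 to 1.0% and the power gain in the strong cases at 10 to 13 points. Even with free imbalance a power gain remains (42.7 vs 53.4% for 20%/70% → 50%/95%).

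Finally, the missing method for attendance is a gap of its own and does not make the efficiency loss for detection any larger.

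**Conclusion.** The point holds. The strata are used in the design and in no stated analysis, and the pooled Fisher test becomes more conservative as the strata become more prognostic. For strata of 13 and 12 per arm, the cost runs from nothing material (not prognostic) to about 9 to 12 points of power and about 4 points on the lower confidence limit (strongly prognostic).

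These sizes rest on assumed rates and stratum sizes and on close balance within strata; the documents do not show where the trial lies in that range. For attendance the loss cannot be assessed, because no method is named. The change is worth making because it is cheap and serves the pilot's stated estimation aim. The existing test does not give wrong error control. Confidence is medium.

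**What to change.** For attendance (months 0–6, and both windows) and for detection (month 6 and month 12):

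1. Report the Mantel-Haenszel risk difference with a 95% CI, stratified by the randomisation strata.
2. Test with an exact conditional test stratified the same way.
3. Name this as the method for the primary attendance outcome.
4. If a clinic-by-abnormality cell has no child in one arm, pool clinics within the abnormality stratum.
5. Keep the pooled Fisher test as a sensitivity analysis.

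The document is written in the past tense. If results have already been analysed, present this as a labelled supplementary analysis.

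**Cost:** SAP wording and a few lines of code, on variables already needed for randomisation.

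**Downsides:**

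- The pooling rule has to be specified.
- The exact stratified test stays conservative (type I error about 2 to 3%, lower with rare events).
- It can lose 1 to 3 points of power when events are rare and the strata are not prognostic.
- The Mantel-Haenszel interval covered 93 to 95% in the power scenarios at this sample size.

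### Fisher's exact test, named for the two secondary detection comparisons, is valid but conservative at 25 per arm, and no effect estimate or interval is planned beside it

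*Combined protocol and SAP*

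**What the plan says.** The Statistical analysis paragraph of the combined protocol and SAP compares detection of a new birth defect or neurodevelopmental abnormality between arms "from baseline to month 6 and baseline to month 12 using Fisher's exact tests". Under Data elements, detection is a secondary outcome. The primary outcome is attendance at one or more "routine pediatric appointment in months 0–6 post-randomization", and no test is named for it. The only other tests named are descriptive: "Participant sociodemographic and clinical characteristics were summarized by intervention allocation with Chi-square tests and t-tests". The analysis is by intention to treat.

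Under Intervention design, 50 dyads are randomised, 25 to each arm, and the number is defended as "consistent with recommendations for randomized pilot studies for preliminary estimation of effect sizes and lower bounds". The document gives no significance level, sidedness, power, expected event rate or target difference. The Statistical analysis paragraph mentions neither an effect measure nor a confidence interval.

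**The concern.** There are two separate issues.

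First, Fisher's test conditions on the total number of events. With 25 per arm and few events, only a handful of p-values can occur, so a nominal 5% test can operate well below 5%. A small trial then gives up some power, and a real difference is more likely to be reported as null.

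Second, Fisher's test by itself yields a p-value. The trial was sized to give effect sizes and lower bounds, and a p-value supplies neither. This mismatch can be read directly from the text and needs no assumption about rates or alpha.

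**Working it through.** **Inputs.** From the document: 25 v 25, Fisher's exact test, two time points. Assumed, because the document is silent: two-sided 5% and the event rates. The plan gives no power or error figure to reproduce.

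**Coarseness, by hand.** With all events in one arm, the two-sided Fisher p at 25 v 25 is 2 × C(25,m)/C(50,m), where m is the total number of events.
- 0 v 4: 2 × 12,650/230,300 = 0.110
- 0 v 5: 2 × 53,130/2,118,760 = 0.0502
- 0 v 6: 2 × 177,100/15,890,700 = 0.022

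So Fisher cannot reach 5% with five or fewer events in total, however they split.

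**True error rate.** Enumerate all 26 × 26 tables. With b(·; 25, p) the binomial probability and P(x, y) the two-sided Fisher p-value (the sum of all conditional table probabilities no larger than the observed one):

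size(p) = Σ b(x; 25, p) · b(y; 25, p), summed over tables with P(x, y) ≤ c.

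Fisher uses c = 0.05. Boschloo uses the largest c for which size(p) stays at or below 5% for every p; at 25 v 25 this is c = 0.0792. Thus 0 v 5 is rejected by Boschloo and 0 v 4 by neither test.

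| Common event rate | Fisher | Boschloo |
|---|---|---|
| 5% | 0.08% | 0.4% |
| 10% | 0.9% | 1.9% |
| 20% | 2.2% | 3.8% |
| 30% | 2.3% | 4.5% |
| 50% | 3.3% | 3.7% |
| Maximum over all rates | 3.3% | 4.6% |

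**Power at 25 v 25.** This is the same sum with a different rate in each arm.

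| Rates | Fisher | Boschloo | Gain (points) |
|---|---|---|---|
| 5% v 10% | 1.3% | 3.2% | 1.9 |
| 5% v 20% | 19.8% | 26.8% | 7.0 |
| 10% v 30% | 30.5% | 38.6% | 8.1 |
| 10% v 40% | 59.1% | 69.0% | 9.9 |
| 30% v 60% | 50.6% | 53.5% | 2.9 |
| 30% v 70% | 78.2% | 79.3% | 1.1 |
| 50% v 80% | 51.0% | 60.6% | 9.6 |

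With both rates between 3% and 97%, the largest gain is 11.3 points (15% v 43%).

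**Sensitivity to the split.**
- At 24 v 25, Fisher's maximum error rate rises to 4.4% (Boschloo 4.6%). Power goes from 32.1% to 35.6% for 10% v 30%, from 57.1% to 60.4% for 50% v 80% and from 54.2% to 54.5% for 30% v 60%: gains of 3.5, 3.3 and 0.3 points.
- At 24 v 26, 5% v 20% gains 0 or about 10 points, according to which arm has the higher rate.
- At 22 v 22, gains can be larger: 54.6% to 66.3% for 10% v 40%, and 39.7% to 52.1% for 30% v 60%.

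At every size checked, Boschloo's rejection region contained Fisher's, so it lost no power.

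**Does a score interval agree with the test?** Not always. For 0/25 v 4/25 the Miettinen–Nurminen statistic is 2.06, so the 95% interval excludes zero, yet Boschloo does not reject. The same happens at 1 v 6, 3 v 9 and 7 v 14. Used as a test, that interval has a maximum error rate of 6.5%.

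**The case against.** The strongest reply is that the plan contains no error. Fisher's test controls type I error, suits a sparse binary outcome and is familiar. It is attached only to secondary outcomes of a pilot meant for estimation, and the document sets no significance-based decision rule. All of this stands: the point is one of efficiency and reporting.

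A second reply is that the remedy helps least where events are rarest. This also stands. At a 5% common rate Boschloo's own error rate is only 0.4%, and at 5% v 10% its power is 3.2%. The gains near 10 points mostly arise at rates that are not sparse, and nothing in the document says which rates to expect for new abnormalities.

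A third is timing. The document is dated August 2023 and describes its analyses in the past tense. Choosing the more powerful test after seeing outcomes would not be sound. This limits the test substitution but not the addition of an estimate and interval.

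A reader might infer that the trial loses about 10 points of power throughout. The document gives no rates to support that, and losing a single outcome from one arm shrinks many of the gains. A reader might also infer that the primary comparison is affected, but Fisher's test is not assigned to attendance. The missing test there is a separate and larger gap. Finally, mid-P may look like an easy substitute, but it does not guarantee control of the error rate.

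**Conclusion.** The point holds as a modest improvement. At 25 v 25 and an assumed two-sided 5%, Fisher's true error rate is at most 3.3% and under 1% at event rates of 10% or less. Boschloo's test keeps exact control (maximum 4.6%) and gains from near 0 to about 10 points of power, slightly more for some rates and splits. The size of the gain rests on assumed event rates and on the final numbers analysed, so no single figure should be quoted for this trial. The firmer half is the absence of any effect estimate or interval in a trial whose size was justified by estimation. The document does not support calling Fisher's test wrong or the primary analysis compromised.

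**What to change.** For each of the two detection comparisons:

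1. Report the risk difference with a 95% confidence interval as the main result. An exact unconditional interval constructed to agree with the test is preferable. If a score interval is used, state that the test governs significance, since the two can disagree.
2. State the significance level and sidedness.
3. If the test can still be fixed before outcomes are seen, specify Boschloo's exact unconditional test in place of Fisher's, and keep Fisher's p-value as supportive. If outcomes have been seen, keep Fisher's as planned and show Boschloo's beside it, labelled post hoc.

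The cost is a sentence or two in the SAP and standard software, with no extra participants or data. The downsides are small: Boschloo's test is less familiar to readers, and the gain may turn out slight.
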